5.4 Study Endpoints

Primary Safety Endpoints:

- Frequency, duration, and intensity of solicited local adverse events (AEs), including pain, redness, and induration for 7 days following each study treatment (for Days 1-3, Days 4-7 and Days 1-7).
- Frequency, duration, and intensity of solicited systemic adverse events (AEs), including fever, nausea, chills, diarrhoea, headache, fatigue, and myalgia for 7 days following each study treatment (for Days 1-3, Days 4-7 and Days 1-7).
- Frequency, duration, intensity, duration, and relatedness of unsolicited AEs through to Day 57. Frequency of Serious Adverse Events (SAEs), Medically-Attended Adverse Events (MAAEs), and any AEs leading to study withdrawal (including decision by the Principal

Investigator (PI) not to proceed with the second dose) at any time during study through to Day 394. Frequency and intensity of unsolicited AEs through to Days 57, 209, and 394

Primary Immunogenicity Endpoints:

- Geometric mean titre (GMT) of the serum antibody response to the Sclamp antigen compared to placebo by antigen specific ELISA at Day 29 (28 days after first dose) and Day 57 (28 days after second dose).
- GMT of the serum NAb titres to SARS-CoV-2 virus compared to placebo by MN assay at Day 29 (28 days after first dose) and Day 57 (28 days after second dose).

Secondary Immunogenicity Endpoints:

- Proportion of subjects with ≥ 4 fold increase in titre above baseline by ELISA at Days 15, 29, 43, 57, 209, and 394 post-first study treatment administration compared to placebo.
- Proportion of subjects with ≥ 4 fold increase in titre above baseline by MN assay at Days 15, 29, 43, 57, 209, and 394 post-first study treatment administration compared to placebo.
- GMT of the serum antibody response to the Sclamp antigen compared to placebo by antigen specific ELISA at Days 1, 15, 29 (28 days after first dose), and Days 43, 57 (28 days after second dose) and Days 209 and 394 (6 and 12 months post-second dose respectively).
- GMT of the serum NAb titres to SARS-CoV-2 virus compared to by MN assay at Days 1, 15, 29 (28 days after first dose), and Days 43, 57 (28 days after second dose) and Days 209, 394.

Exploratory Immunogenicity Endpoints:

- Proportion of subjects experiencing laboratory confirmed SARS-CoV-2 infection and/or severity graded COVID-19 disease between Days 57 and 394 compared to placebo.

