The study will evaluate a single formulation of SARS-CoV-2 Sclamp protein subunit vaccine administered as a single dose or two doses of varying vaccine antigen concentrations in distinct cohorts.

Four treatments (A, B, C, and D) will be administered to subjects.

This study will consist of 6 cohorts: 2 cohorts of a lower dose (Treatment A), 2 cohorts of an intermediate dose (Treatment B), 1 cohort of a higher dose (Treatment C)(Part 2 only), and 1 cohort of a higher dose, examining both a two dose regimen (Treatment C) and a single dose vaccination regimen (Treatment D) (Part 1 only).

Cohorts 1,2 and 3 will include subjects aged ≥ 18 - ≤ 55 years of age and cohorts 4, 5 and 6 will include subjects aged 56 years and older. Cohorts 4, 5 and 6 will include an approximately equal number of subjects aged ≥ 56 - ≤ 65 years of age, and ≥ 66 years and over.

Part 1: Cohort 1 will include 32 subjects; of these 8 will receive placebo, and 24 subjects will receive Treatment A. Cohort 2 will include 32 subjects; of these 8 will receive placebo, and 24 subjects will receive Treatment B. Cohort 3 will include 56 subjects; of these 8 will receive placebo, 24 subjects will receive Treatment C, and 24 subjects will receive Treatment D.

Part 2: Cohort 4 will include 32 subjects; of these 8 will receive placebo, and 24 subjects will receive Treatment A. Cohort 5 will include 32 subjects; of these 8 will receive placebo, and

24 subjects will receive Treatment B. Cohort 6 will include 32 subjects; of these 8 will receive placebo, and 24 subjects will receive Treatment C.

Treatment	Dose regimen
Treatment A (Cohorts 1 & 4)	SARS-CoV-2 Sclamp vaccine 1 x 5 mcg, or placebo, administered in a two dose regimen, at least 28 days apart
Treatment B (Cohorts 2 & 5)	SARS-CoV-2 Sclamp vaccine 1 x 15 mcg, or placebo, administered in a two dose regimen, at least 28 days apart
Treatment C (Cohorts 3 & 6)	SARS-CoV-2 Sclamp vaccine 1 x 45 mcg, or placebo, administered in a two dose regiment, at least 28 days apart
Treatment D (Cohort 3 only)	SARS-CoV-2 Sclamp vaccine 1 x 45 mcg, or placebo, administered as a single dose, followed by placebo as the second dose at least 28 days apart

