9.4 Allocation of Subjects to Treatment

Subjects will be randomly assigned a 4-digit randomisation number beginning by "1", "2", "3", "4", "5" and "6" for Cohorts 1, 2, 3, 4, 5 and 6 respectively. Each subject number corresponds to a treatment assignment on the generated randomisation scheme.

For Part 1 (healthy adults), the two sentinel subjects of each cohort will have the first two subject numbers of their cohort e.g. 1001 and 1002 for Cohort 1, and 2001 and 2002 for Cohort 2 and 3001 and 3002 for Cohort 3. In the case where a subject is replaced (following specifications described in Section 9.13), the replacement volunteer will take the same treatment and the same subject number added with 100. For example, if the subject number 1001 withdrew, the replacement subject will have the subject number 1101, with the treatment planned for the randomization number 1001.

For Part 2 (healthy older adults), subjects will be randomly assigned to treatment groups in a 3:1 ratio of Active to Placebo. The randomisation will be stratified by age (≥ 56 to ≤ 65 years, and ≥ 66 years respectively).

For subjects who are replaced, the replacements should take the same treatment assignment as the original subject to ensure that the planned treatment allocation ratio is retained.

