The analysis model for the Sclamp antibody, or the MN GMTs, will be performed using a general linear model on log-transformed (base 10) post-GMT titres as the outcome variable and as covariates such as treatment groups (dose) and log-transformed pre-vaccination titre. Model adjusted differences in means (on the log scale) will be produced with 95% confidence limits. The estimated difference between treatment groups and the confidence limits will be back-transformed to obtain an *adjusted* GMT ratio with 95% confidence limits.

The measure of the *unadjusted* GMT ratio based on post-vaccination GMT only will also be presented.

In addition, reverse cumulative distribution plots will be generated to display the distribution of the antibody response at Days 29 and 57 for the active study phase, and will be explored for Days 209 and 396 (follow-up phase). Baseline titres for serum antibody to Sclamp, and MN titres to SARS-CoV-2 virus, will be less than or equal to the lower limit of quantitation (\leq LLOQ) and will be imputed as $\frac{1}{2}$ LLOQ.

Bioanalysis of all samples up to, at least, Day 57 should be completed prior to the initiation of the immunogenicity and statistical analyses.

As the SARS-CoV-2 Sclamp study vaccine does not contain novel adjuvants nor excipients, and it is not administered via a novel delivery system nor route of administration, no pharmacokinetic analyses will be conducted in agreement with the EMA Guideline on Clinical Evaluation of New Vaccines.⁵

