11.2 Immunogenicity

Various approaches will be used in this study to assess the immunogenic response of the SARS-CoV-2 Sclamp vaccine in subjects: analysis of SARS-CoV-2 specific immune response via ELISA, analysis of domain specificity and immunoglobulin isotype induction via Luminex Assay, analysis of MN assessed via virus neutralisation, and ADCC via a bioluminescent reporter assay. Additionally, induction of poly-functional T-cells will be assessed via stimulation of PBMCs with vaccine specific antigen, and further analysed via various staining techniques coupled with multi-flow cytometry. While analysis of safety and tolerability is the primary outcome of this study, the combination of immunogenicity data collected will provide some indication of the potential efficacy of the vaccine for future studies to investigate further.

Seroconversion rate is defined as a minimum 4-fold rise in post-vaccination titre at Days 29 and 57 relative to Day 1. The baseline titres for serum antibody to Sclamp and MN titres to SARS-CoV-2 virus will be \leq LLOQ and will be imputed as $\frac{1}{2}$ LLOQ.

Blood samples will be collected at specified visits according to the Schedule of Assessments included in Section 4, and blood volumes will be collected according to Section 9.9.

The immunogenicity analyses will evaluate immunogenicity of SARS-CoV-2 Sclamp vaccine as measured by ELISA and MN assay.

Additional immunologic assays, including ADCC reporter assay and Luminex assay will be used to conduct further exploratory analysis to determine antibody isotypes, domain specificities and functions that may be correlated with protection.

Potential for seroconversion to trigger false positives on HIV testing will be assessed by assessing blood samples in a panel of point of care and investigative HIV detection diagnostics.

Serum samples will be analysed by Sponsor designated qualified laboratory personnel blinded to the treatment assignment and the visit. Please see Laboratory Manual for complete details.

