11.5 Immunogenicity Analysis

For the evaluation of immunogenicity, vaccine antibody titres will be analysed using the Immunogenicity Population and the methodology described previously in Section 11:

- Geometric Mean Titres (GMT) on Days 1, 15, 29, 43 and 57, and 209 and 394 will be summarized using descriptive statistics by treatment group compared to placebo;
- Seroconversion on Days 15, 29, 43, 57, 209 and 394, compared to placebo. Seroconversion is defined as the percentage of subjects with a ≥ 4 fold increase in post-vaccination titre compared to Day 1;
- Geometric Mean Fold increases on Day 15 / Day 1, Day 29 / Day 1, Day 43 / Day 1, and Day 57 / Day 1, Day 209 / Day 1, and Day 394 / Day 1, compared to placebo;
- Fold increase in antigen specific CD4+ T-cells at Days 8, 15, 29, 36, 43, and 57 compared to Day 1 for vaccine antigen dose versus placebo;
- Fold increase in antigen specific CD8+ T-cells at Days 8, 15, 29, 36, 43, and 57 compared to Day 1 for vaccine antigen dose versus placebo;
- Fold increase in antibody dependent cellular cytotoxicity (ADCC) at Days 15, 29, 43, 57, 209, and 394 compared to Day 1 for vaccine antigen dose versus placebo;
- Fold increase in antibodies elicited to the Receptor Binding Domain (RBD), N-Terminal Domain (NTD), and clamp trimerization domain on Days 15, 29, 43, 57, 209, and 394 compared to Day 1 for vaccine antigen dose versus placebo; and
- Fold increase in antigen specific humoral immune responses including isotypes IgM, IgA, IgE, and subtypes IgG1, IgG2, IgG3 and IgG4 at Days 15, 29, 43, 57, 209, and 394 compared to Day 1 for vaccine antigen dose compared to placebo.

Once all subjects have completed Day 57, an interim analysis will be performed. The immunogenicity analysis will be included as part of this interim analysis.

12. Final Report

A final report including clinical, bioanalytical, and statistical sections will be the responsibility of Delve Medical Writing and will be signed and approved by at least the Sponsor.

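### Under the protocol's own half-LLOQ rule the only covariate named besides treatment in the GMT model is constant, so it adjusts nothing, while the Part 2 age stratum is not named

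*Protocol*

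**What the plan says.** Section 11 (Statistical Analyses), repeated in the Synopsis, sets a general linear model on log10 titre with "post-GMT titres as the outcome variable and as covariates such as treatment groups (dose) and log-transformed pre-vaccination titre". The back-transformed group difference is the adjusted GMT ratio, and an unadjusted "GMT ratio based on post-vaccination GMT only will also be presented".

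The same section says that baseline ELISA and microneutralisation titres "will be less than or equal to the lower limit of quantitation" and are imputed as half the LLOQ. Section 11.2 repeats this: "The baseline titres for serum antibody to Sclamp and MN titres to SARS-CoV-2 virus will be" at or below the LLOQ, with the same imputation. Exclusion criterion 3 (Section 8.4) removes antibody-positive subjects, so this is the expected state of the data.

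Section 11.5 adds "Geometric Mean Fold increases on Day 15 / Day 1, Day 29 / Day 1" and later days, compared with placebo. The primary immunogenicity endpoints in Section 5.4 are GMTs against placebo at Days 29 and 57, for example "GMT of the serum NAb titres to SARS-CoV-2 virus compared to placebo by MN assay at Day 29".

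For Part 2, Section 9.4 states: "The randomisation will be stratified by age", with strata 56 to 65 years and 66 years and over. Section 6 adds "Cohorts 4, 5 and 6 will include an approximately equal number of subjects aged" in each of these two ranges. Age is not mentioned in the model text of Section 11 or the Synopsis, nor in Section 11.5.

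**The concern.** A covariate adjusts only if it varies. Here the protocol names one covariate besides treatment and, in the same section, gives it the same value for everyone. A reader who sees matching adjusted and unadjusted ratios for the primary immunogenicity endpoint could take the match as a sign of robustness, when it is guaranteed by construction.

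A variable that could carry information is known for every Part 2 subject, because randomisation uses it. If titre differs between the two age strata, a model without the stratum leaves that difference in the residual variance. With 24 subjects per active group and no power calculation (Section 8.2), and with dose and regimen to be chosen partly on immunogenicity (Section 11.3), precision that costs almost nothing is worth having.

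The baseline sentence also states an expectation as a fact and does not say what happens to a measured baseline above the LLOQ.

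**Working it through.** **Inputs.** Model terms and baseline rule: Section 11, Section 11.2 and Synopsis. Part 2 group sizes: 24 on each of A, B and C, and 8 placebo per cohort, so 24 if pooled (Section 8.2). Strata: Section 9.4. The protocol gives no SD, LLOQ, age effect or power, so there is no figure of its own to reproduce.

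**Step 1: the constant covariate.** Write y for log10 post-vaccination titre and b for log10 baseline. The model is y = (group mean) + βb + error. If b = log10(LLOQ/2) = k for all subjects, βk is the same for everyone and cancels from every group difference.

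- Design rank with 96 Part 2 subjects: treatment only, 4 of 4 columns; with the constant baseline added, 4 of 5. Residual df = 96 − 4 = 92 both ways, and β is not estimable.
- Illustration (assumed LLOQ 20, SD 0.5 log10, age difference 0.3 log10; the equality does not depend on these values). Ratios to placebo, with and without baseline: A 6.539 (3.506–12.197), B 16.526 (8.860–30.824), C 25.468 (13.654–47.504). Both fits give the same figures.
- Fold increase: log(post/baseline) = y − k, so its ratio to placebo has the same point estimate.
- What can differ: if the unadjusted ratio uses a separate two-group t interval, C becomes 25.468 (14.461–44.853). One detectable baseline among the 96 moves C from 25.47 to 25.51.

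**Step 2: the age stratum, with arm-specific variances.** Let R² be the share of active-arm log-titre variance explained by the stratum (assumed 5, 10 or 20%), with 12 subjects per stratum per active arm. After balanced stratified randomisation the true variance of a dose-versus-dose difference is (1 − R²) times what a model without the stratum estimates. In large samples:

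- coverage without the stratum = 2Φ(1.96/√(1 − R²)) − 1 = 95.6/96.1/97.2%
- narrowing from including it = 1 − √(1 − R²) = 2.5/5.1/10.6%

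Simulation (100,000 trials, Satterthwaite df; the stratified interval averages the two stratum-specific differences), at R² = 5/10/20%:

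| Contrast | Coverage without (%) | Coverage with (%) | CI narrower by (%) |
|---|---|---|---|
| Dose v dose, 24 v 24 | 95.4/96.0/97.2 | 94.8/95.0/95.0 | 2.5/5.2/10.9 |
| Dose v 24 placebo, placebo SD half of active, no age effect in placebo | 95.5/95.9/96.7 | 95.1/95.0/95.0 | 2.0/4.2/8.7 |
| Dose v 8 placebo, same assumptions | 95.3/95.8/96.3 | 95.0/95.1/95.0 | 0.8/2.1/5.0 |

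If R² = 0, including the stratum widens intervals by 0.1–0.2% (24 placebo) or 0.2–1.5% (8 placebo).

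**Step 3: one common residual variance.** An ordinary general linear model pools variance over arms, and placebo titres may hardly vary. With active SD 1 and placebo SD 0, the pooled variance is (69 × 1 + 23 × 0)/92 = 0.75. Dose-versus-dose coverage without the stratum is then about 2Φ(1.96 × √0.75/√(1 − R²)) − 1 = 91.8/92.6/94.2%. Simulation gives 92.0/92.8/94.4%, and 93.2/93.9/95.1% with placebo SD 0.5. Dose-versus-placebo coverage at placebo SD 0 is 98.5/98.7/99.3%. Adding the stratum alone, again at placebo SD 0, lowers dose-versus-dose coverage to about 91–92%, because it removes the excess variance that was partly masking the shortfall.

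**The case against.** The strongest reply is that the covariate list is open and that Section 11 leaves the full methods to an SAP, which overrides the protocol. This stands against any claim that age will be left out of the analysis; a reader might infer that, and the protocol does not show it. It does not rescue the covariate that the protocol does name.

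Second, the baseline sentence may be an expectation joined to a rule for titres at or below the LLOQ, not an order to overwrite higher ones. Higher values are possible: Section 9.10.6.7 schedules the antibody ELISA at screening and swab testing only from Day 1, up to 28 days later. Baseline titre would then vary a little. This is fair, and is a reason to state the rule. One such value in 96 barely moves the result.

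Third, nothing is biased and the study has no formal success rule (Section 11.3). This also stands.

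Fourth, Section 8.1 speaks of immune decline with age in order to compare younger with older adults. It gives no evidence of a difference between 56–65 and 66 and over. That is right, so the R² values are assumptions and zero is possible.

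Two stronger readings are not supported. One is that the adjusted ratio, unadjusted ratio and fold increase are a single result: their intervals can differ through the error term, and within-group fold increases are ordinary descriptive output. The other is that leaving out the stratum only makes intervals conservative: this fails for dose-versus-dose contrasts when variance is pooled with a low-variance placebo group.

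**Conclusion.** The point holds in a limited form. If all baselines are at or below the LLOQ, as the protocol states, the named covariate is constant and the adjusted ratio repeats the unadjusted point estimate exactly. This is algebra and needs no assumed SD, LLOQ or effect.

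The missing age stratum is the weaker half, because the SAP may supply it. Its value is modest and rests on the assumed R², on equal strata and on arm-specific variances: about 2.5/5/11% narrower dose-versus-dose intervals, and about 1–5% against a cohort's own 8 placebo subjects at half the active SD. Under a common variance with near-constant placebo titres, dose-versus-dose intervals are already too narrow, and the stratum alone does not repair that. The two model changes therefore belong together. Severity is minor to moderate: worth correcting, with no threat to validity from the constant covariate itself.

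**What to change.** In Section 11 and the Synopsis:

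1. Name the randomisation age stratum (56–65, 66 and over) as a covariate in the Part 2 GMT model, for dose-versus-placebo and dose-versus-dose contrasts. Let the residual variance differ between arms, at least between placebo and active. The gains above come from averaging the two stratum-specific differences, which lets the age effect differ between arms.
2. Keep log pre-vaccination titre only if it varies.
3. Replace the imputation sentence, also in Section 11.2, with: *Baseline titres at or below LLOQ will be imputed as half LLOQ; quantifiable baseline titres above LLOQ will be analysed as measured.* Keeping the boundary at or below matters. For a baseline equal to the LLOQ, the 4-fold threshold is 4 × LLOQ/2 = 2 × LLOQ; imputing only values below the LLOQ would move it to 4 × LLOQ and so alter a secondary endpoint.

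The cost is wording and a few degrees of freedom. If age explains nothing, intervals widen by up to about 1.5% with 8 placebo subjects and by 0.1–0.2% with 24. No new data are needed.

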11.1 Safety Measurements

Safety will be assessed by measuring the frequency and intensity of local and systemic solicited adverse events (AEs), unsolicited AEs, serious adverse events (SAEs), and safety laboratory data for all subjects. All solicited adverse events will be summarised according to the protocol defined severity grading scales. The proportion of subjects experiencing each adverse event will be presented for each symptom severity. Summary tables showing the occurrence of any local or systemic adverse event overall and at each time point will be presented.

Reactogenicity will be assessed by the proportion of subjects with solicited local and solicited systemic AEs up to 7 days after each vaccination and calculated for 3 time intervals after each vaccination: Days 1--3, Days 4--7, and Days 1--7. Post-administration solicited adverse events reported from Days 1-7 will be summarised by time interval, maximal severity and by vaccine group. The severity of solicited local adverse events, including injection site redness, swelling and induration will be summarised according to categories based on linear measurement: 2.5 to 5.0 cm, 5.1 to 10.0 cm and >10 cm.

Injection site pain and systemic reactions (except fever) occurring up to 7 days after each vaccination dose will be summarised according to “mild”, “moderate” or “severe”. Body temperature will be summarised by 0.5 °C increments from 36.0 °C up to ≥ 40 °C and will be reported by route of measurement.

Unsolicited AEs will be assessed by the proportion of subjects with any unsolicited AEs for 28 days after each vaccination.

The proportion of subjects with SAEs, TEAS, non-scheduled GP visits, unsolicited medically attended AEs, unsolicited AEs leading to study withdrawal or decision by the PI to discontinue with the second dose, will be collected from study start until study completion.

All spontaneously reported adverse events occurring during the study assessed by the Investigator as probably related, possibly related, or not related to vaccination will be recorded.

The original terms used by the Investigator in the CRFs will be assigned to preferred terms using the MedDRA dictionary. The adverse events will then be grouped by MedDRA preferred terms into frequency tables according to system organ class and preferred terms within each system organ class then presented by vaccination group. Where an adverse event occurs more than once for a subject, the maximal severity and strongest relationship to the vaccine group will be counted.

Separate summaries will be prepared as follows:

- Serious adverse events
- Adverse events that are probably or possibly related to the vaccine
- Adverse events leading to a medically attended visit

Safety parameters, ie.laboratory parameters, ECG and vital signs, will be assessed by the PI or delegate, using the clinical site’s criteria for acceptance ranges as guidelines in making the medical assessment. Abnormal safety blood and urinalysis laboratory measurements will be assessed for severity in accordance with the scoring system described in the FDA Guidance for Industry – Toxicity Grading Scale for Healthy Adults and Adolescent Volunteers Enrolled in Preventive Vaccine Clinical Trials(4) using the reference ranges specified by the testing laboratory, SydPath in accordance with the Laboratory Manual.

Safety measurements which in the opinion of the investigator are deemed clinically significant will be recorded as adverse events

